# Fluticasone Propionate and Salmeterol Inhalation Powder Protocol No. 71736001

occasion at two different sites will be tracked as "Double Dippers." All Double Dippers will be reviewed and evaluated for efficacy analysis prior to database lock.

Modified Intent-to-Treat (mITT) Population	
Safety Populations	

#### 8. STATISTICAL ANALYSIS METHODS

If not otherwise specified, statistical significance is defined as p < 0.05 and is two-tailed. Data will be summarized with respect to demographic and baseline characteristics and safety variables.

In general, all data will be listed by subject and visit/time point where appropriate. The summary tables will be stratified by, or have columns corresponding to, treatment groups. The total number of subjects in the treatment group (N) under the stated analysis set will be displayed in the header of summary tables. For categorical variables, the number and percentage of each category within a parameter will be calculated for non-missing data. In summary tables of categorical variables,

#### Fluticasone Propionate and Salmeterol Inhalation Powder Protocol No. 71736001

counts and percentages will be displayed. The count [n] indicates the actual number of subjects in a particular category, which should always be less than or equal to the total number of subjects in the respective study group with known (non-missing) category [M]. Percentage will be obtained by: % = n/M\*100. Unless otherwise specified, all percentages will be expressed to one decimal place.

For continuous variables, statistics will include n, mean, standard deviation, median, minimum and maximum values. The minimum and maximum statistics should be presented to the same number of decimal places as the original data. The mean and median should be presented to one more decimal place than the original data. The standard deviation should be presented to two more decimal places than the original data.

All statistical analyses will be conducted using SAS®, Version 9.4 or higher. Datasets will be prepared using headings from Clinical Data Interchange Consortium (CDISC), Study Data Tabulation Model (SDTM) implementation for human clinical trials, and ADaM (Analysis Dataset Model).

#### 8.1 Baseline Characteristics

#### 8.1.1 Subject Disposition

The subject disposition information will be summarized. The number of subjects enrolled, randomized will be tabulated. In addition, completion status and primary reason for withdrawal will be summarized.

### 8.1.2 Demographic and Other Baseline Characteristics

The following subject demographic characteristics will be summarized separately in the

- Age (years) (Age will be derived from ICF date relative to birth date)
- Sex (Male/Female)
- Ethnicity (Hispanic/non-Hispanic)
- Race (White, Black/African American, Native Hawaiian or Other Pacific Islander, Asian, American Indian or Alaska Native)
- Number of years subject has suffered from symptoms caused by asthma
- Pre-dose Baseline FEV1
- Height (cm)
- Weight (kg)
- BMI  $(kg/m^2)$

Summary tables by treatment group will be presented. Continuous variables will be summarized using descriptive statistics (number of observations, median, minimum, maximum, mean, and SD). Categorical variables will be summarized using frequencies and percentage. Baseline

#### Fluticasone Propionate and Salmeterol Inhalation Powder Protocol No. 71736001

treatment comparisons will be presented using Chi-Square or Cochran-Mantel-Haenszel tests for the categorical variables, and Analysis of Variance (ANOVA) for the continuous variables.

All data will be listed by treatment and subject.

#### 8.1.3 Medical History

At Visit 1, subjects will be questioned about medical history, including smoking history, acute and chronic medical history, and medical history relevant to their asthma. Medical history data will be listed for asthma history and for non-asthma medical history by treatment and subject, respectively. These analyses will be done for the Safety Population Randomized.

#### 8.1.4 Prior and Concomitant Medications

At Visit 1, subjects will be questioned about medication use over the previous 6 months. At all subsequent visits, subjects will be questioned about ongoing or new concomitant medication use.

Prior and concomitant medication will be coded according to the World Health Organization — Drug Reference List and the Anatomical Therapeutic Chemical classification system or similar. Prior medications are defined as those taken before the first dose of randomized study drug on Day 1 (i.e., start and end date before the first dose of randomized study drug). Concomitant medications are defined as those taken at the time of or after the first dose of randomized study drug. Any medications that were started before the first dose of randomized study drug on Day 1 but continued after dosing will be considered a concomitant medication.

Concomitant medications will be summarized by treatment group. ATC class (highest level available) and preferred name. This analysis will be done for the

All prior and concomitant medications taken since screening until the end of the study will be listed by treatment group and subject.

#### 8.2 Efficacy Analyses

#### 8.2.1 Calculation of the Primary Endpoints

# Acceptability Criteria.

For the purpose of this study, ATS quality will be demonstrated by receiving a quality grade of upon review and only these results will be used for analysis. Results with a quality grade of will be treated as missing in all calculations.

# Fluticasone Propionate and Salmeterol Inhalation Powder Protocol No. 71736001 FEV1 Baseline.

The FEV1 baseline will be defined as the average of the pre-dose FEV1 values obtained at Visit 2 Day 1. If some of these measurements are missing, the average will be calculated using the available measurements, however, a minimum of two pre-dose FEV1 values is required; subjects who have only one or no pre-dose FEV1 measurements on Day 1will have their FEV1 baseline missing, and this the subject will be excluded from analysis.

# Calculation of FEV1 AUC0-12.

The endpoint of Baseline-adjusted FEV1 AUC0-12 on Day 1 will be calculated as follows:

- 1. Each FEV1 assessment on Day 1 will be baseline-adjusted by subtracting the FEV1 baseline value defined above.
- 2. FEV1 AUC0-12 will be calculated from the baseline-adjusted values using the linear trapezoidal method. The calculation will assume that at time of dosing (time 0) the baseline-adjusted FEV1 is also 0. The calculation will proceed over all available postdose FEV1 assessments on Day 1 (including unscheduled timepoints, if any) using actual elapsed time from dosing.
- 3. FEV1 AUC0-12 will be considered non-computable in a subject if one of the following occurs in that subject:

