## **11.0 STATISTICAL METHODS**

## 11.1 Statistical Plan

A statistical analysis plan (SAP), detailing the study populations, intended statistical analysis, and reporting of the study data, will be prepared as a separate document and finalized before database lock. Any deviation from the original statistical plan will be described and justified in the final report, as appropriate. The procedure for accounting for missing, unused and spurious data will be included in the SAP. The SAP will take precedence over what is outlined in the protocol, if differences are noted.

All statistical analysis will be conducted using SAS®, Version 9.4 or higher. Datasets will be prepared using headings from Clinical Data Standards Interchange Consortium (CDISC) Study Data Tabulation Model implementation for human clinical trials and Analysis Dataset Model.

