## **11.5 Efficacy Endpoints**

The two co-primary efficacy endpoints are (1) the baseline-adjusted area under the serial FEV1-time curve calculated from time zero to 12 hours (AUC0-12h) on Day 1 of treatment (Visit 2), and (2) the baseline-adjusted pre-dose FEV1 measured in the morning of Day  $29 \pm 2$  (Visit 3), after the last dose in the prior evening.

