#### Randomization

Subjects who meet all inclusion/exclusion and randomization criteria at Visit 2 will be randomized to study product in a ratio (Test: Reference: Placebo). Serial pulmonary function tests will be performed over 12 hours at Visit 2. FEV1 should be measured at approximately the first dose of study product and approximately 30 minutes, 1, 2, 3, 4, 6, 8, 10, and 12 hours post-dose. The second dose of study product will be administered after the 12-hour FEV1 is collected. At least two of the pre-dose time point FEV1 measurements must meet ATS criteria for quality in

Fluticasone Propionate and Salmeterol Inhalation Powder	Protocol No.	71736001
order to establish a baseline value. The average of the quality $FEV_1$ to determine the baseline $FEV_1$ , which must be $\geq 40\%$ and $\leq 85\%$ of p may not vary by more than from the qualifying Screening vis the subject to be eligible for inclusion in the study.	predicted norma	l value and
End of Study		
The final time points $FEV_1$ measurements will be collected a should take place at the same time of day as the pre-dose Visit 2 ( $\pm$ 2 hours). The remaining $FEV_1$ measurements should be confollowing the preceding measurement.	measurement,	_
ronowing the preceding measurement.		
The last dose of study product sho evening before Visit 3.	uld be administ	ered on the
Subjects should not administer the rescue medication, or study produc study visit.	t within 6 hours	before any

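### Does the Day 1 FEV1 AUC0-12h co-primary need an explicit rule for ending the integration at exactly 12.00 h?

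*SAP*

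**What the plan says.** Protocol 11.5 defines the first co-primary as the baseline-adjusted area under the Day 1 serial FEV1 "time curve calculated from time zero to 12 hours", and SAP section 6 repeats that definition. Under the SAP's Randomization heading (section 3), readings are taken at "approximately 30 minutes, 1, 2, 3, 4, 6, 8, 10, and 12 hours post-dose". The same paragraph places the evening dose later: "The second dose of study product will be administered after the 12-hour" reading.

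SAP 8.2.1 gives the calculation. Baseline is subtracted from each reading, and the start is fixed: "The calculation will assume that at time of dosing (time 0) the baseline-adjusted" value is zero. The linear trapezoidal rule is then applied to every available post-dose value, that is, to "assessments on Day 1 (including unscheduled timepoints, if any) using actual elapsed time from dosing". Step 3 says that the AUC "will be considered non-computable in a subject if one of the following occurs in that subject", but the list of conditions is blacked out, as is Appendix A. Protocol 11.1 adds: "The SAP will take precedence over what is outlined in the protocol, if differences are noted".

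**The concern.** The lower limit of integration is explicit and the upper limit is not. Sampling times are approximate and actual times are used, so few last readings will fall at exactly 12.00 h. A literal program would give AUC0-11.6 for one subject and AUC0-12.4 for another under the same label. Even an analyst who treats 12 h as a hard limit is not told in the readable text how to get the value at 12.00 h from a reading at 12.4 h, or what to do when the last reading is at 11.6 h. An unscheduled Day 1 reading after the second dose would also enter the sum. Because the SAP overrides the protocol, one might think the protocol's 12-hour definition cannot repair this.

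The AUC is one of the two endpoints on which equivalence rests, and it is also tested against placebo. A programming choice that could move the Test/Reference ratio would need to be settled before unblinding.

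**Working it through.** **Does the plan fix the window?** The precedence clause applies only where SAP and protocol differ. On the window they agree: both state 0 to 12 h, and step 2 itself calls the result AUC0-12. Step 2 then says which readings to use and which clock to use. What is left open is how the last partial interval is closed.

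**How large is the effect?** The documents show no AUC, SD or sample size (all blacked out), so there is no figure in the plan to reproduce. The inputs are the nominal times 0, 0.5, 1, 2, 3, 4, 6, 8, 10 and 12 h, a start at (0, 0), and three assumed baseline-adjusted profiles in litres:

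- moderate decline: 0, .25, .33, .38, .40, .40, .38, .34, .31, .28
- flat: 0, .25, .33, .36, .38, .38, .38, .38, .37, .37
- steep decline: 0, .25, .33, .38, .40, .40, .35, .28, .22, .16

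The last reading is moved along the 10-12 h line. The area gained or lost is the time shift times the mean of the value at 12 h and the value at the new time. For the moderate profile at 11.5 h this is 0.5 × (0.28 + 0.2875)/2 = 0.1419, and 0.1419/4.0925 = 3.47%.

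| Profile | AUC0-12 (L·h) | Last reading 11.5 h | Last reading 12.5 h |
|---|---|---|---|
| Moderate | 4.0925 | -3.47% | +3.38% |
| Flat | 4.3125 | -4.29% | +4.29% |
| Steep | 3.6125 | -2.32% | +2.11% |

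At 11.75 or 12.25 h the changes are about half as large, 1.1% to 2.1%.

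**Effect on the mean.** Let the drift be uniform over ±0.5 h, with variance 1/12 = 0.0833 h². The errors cancel except for the curvature term, slope/2 × 0.0833. The steep profile falls 0.03 L per hour, so the shift is 0.015 × 0.0833 = 0.00125 L·h, and 0.00125/3.6125 = 0.035%. The moderate profile gives 0.015% and the flat one 0. If both arms share the drift, the ratio stays at 1.00.

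**Effect on precision.** The drift SD is 0.5/√3 = 0.289 h. Multiplied by the 12 h value and divided by the AUC, this is a CV of 0.289 × 0.28/4.0925 = 2.0% (moderate), 0.289 × 0.37/4.3125 = 2.5% (flat) and 0.289 × 0.16/3.6125 = 1.3% (steep). The worst case is the flat profile (2.48%) with an assumed between-subject CV of 30%. Added independently, √(0.09 + 0.000615) = 0.30102, a rise of 0.34%. If the timing error scales with the subject's response, √(0.09 + 0.000615 + 0.09 × 0.000615) = 0.30112, a rise of 0.37%. For illustration, a confidence-interval half-width of 10 percentage points would become about 10.04.

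**Cross-check.** A separate set of assumed profiles (flat at 0.40 L, slow waning to 0.33 L, fast waning to 0.10 L), with the last value held fixed and only its time moved, gives 1.9% to 4.3% per subject at ±30 minutes. End-time scatter with an SD of 15 minutes takes a CV of 50% to 50.03%.

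**What would bias the ratio?** A timing difference between arms would. If every Test subject were read 15 minutes later than every Reference subject, the slow-waning profile (AUC 4.525) gives 1 + 0.25 × 0.33/4.525 = 1.018. Nothing in the documents suggests such a difference, and SAP section 4 keeps the staff doing spirometry blinded.

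**What would an added rule remove?** Interpolating to 12.00 h, or carrying an 11.5 h value forward, leaves at most 0.1% error on the first three profiles. The gain is therefore removal of the 1.3% to 2.5% timing CV, which the precision check shows to be immaterial.

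**The case for a change.** The strongest case for acting is reproducibility. This is a pivotal endpoint, the SAP is the place to fix its computation, and two competent programmers could return different AUCs for the same subject. The change would be cheap, and conditions that make an AUC non-computable would not by themselves trim a late reading to 12.00 h. It is true that the readable text leaves that convention open.

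The harmful reading can be excluded, however. Discarding a 12.4 h reading as out of range would end the sum at 10 h and lose 0.59/4.0925 = 14.4%, 0.74/4.3125 = 17.2% or 0.38/3.6125 = 10.5% of the area on the moderate, flat and steep profiles. That contradicts the instruction to use all available values, and a reading at 12.4 h is plainly the scheduled 12-hour reading. The other choices (stop at the last reading, interpolate, carry forward) differ by the few percent per subject shown above and are blind to treatment.

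A series that ends well before 12 h is a larger matter. Ending at 10 h costs 7.6% to 17.0% on the second set of profiles. If it happened in 10% of Test and no Reference subjects, the ratio would fall to 0.985 on the slow-waning profile. Whether such a series counts at all depends on the blacked-out conditions in step 3, so it cannot be held against the plan. A reading after the second dose is possible on paper, but none is scheduled.

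**Conclusion.** No change follows. The 0 to 12 h window is stated in both documents and in the name of the quantity. The open point is an end-interval convention that a programmer fills sensibly, and it may already be covered by text that cannot be read. A single subject's AUC can move by about 2% to 4% with a 30-minute deviation. Across subjects the mean shifts by less than 0.04%, the SD rises by less than 0.4%, and the Test/Reference ratio is unaffected.

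This rests on the assumed profiles, drift within about half an hour, a between-subject CV of at least 30%, and timing that does not differ between Test and Reference. The limits of 80.00-125.00% are far wider than anything this timing can produce; even the contrived case of one whole arm read 15 minutes late gives 1.8%. A stated rule would be tidy, but it would alter no conclusion, and carrying early readings forward would itself need a defined tolerance before 12.00 h.

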# Calculation of Baseline-adjusted Pre-dose FEV1 at End of Treatment.

The endpoint of Baseline-adjusted pre-dose  $FEV_1$  at end of treatment will be calculated as  $[FEV_1]$  at end of treatment will be defined as the

If a subject has no pre-dose assessment at Visit 3, Day 29, in the mITT analysis Average  $FEV_1$  at end of treatment will be imputed (following LOCF rule) as the average of available predose assessments on the last post-baseline day (Day 2 through 32) when at least one pre-dose  $FEV_1$  assessment is available (e.g. the Early Termination visit). Only assessments occurring after start of the randomized treatment (Day 2) and up to day will be considered for LOCF. In the PP

Fluticasone Propionate and Salmeterol Inhalation Powder Protocol No. 71736001

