## 10.2.5 Removal of Subjects from the Study

Subjects will be advised that they are free to withdraw from the study at any time for any reason or, if necessary, the Investigator may withdraw a subject from the study to protect the health of that subject. A subject may also be withdrawn for not complying with study procedures. The clinical report will include all reasons for early withdrawals.

If a randomized subject terminates from the study early, all efforts will be made to complete their next scheduled visit to perform all required End of Study/ Early termination visit activities except spirometry that does not need to be performed. In case of early termination the Investigator will fully document the reason for early termination. Reasons for early termination may include the following:

- Subject withdrew consent.
- Significant AE that led the Investigator or subject to withdraw for safety reasons.
- Serious AE, regardless of relationship to study medication.
- Non-compliance with protocol requirements (e.g., use of restricted medication, not following dosing procedures, failure to make scheduled study visits in a timely fashion).
- Pregnancy
- Significant worsening of asthma, defined as a clinically significant exacerbation (see Section 10.2.6) that requires emergency intervention, treatment with restricted medications or hospitalization. Withdrawal of the subject from the study is based on Investigator judgment if he or she believes it is in the best interest of the subject to withdraw from the study and provided alternative treatment.
- Excessive use of rescue albuterol during the study. See Section 10.2.6.

A Randomized, Multiple-Dose, Blinded, Placebo-Controlled, Parallel-Design, Multiple-Center, Clinical Study to Evaluate the Therapeutic Equivalence of Fluticasone Propionate and Salmeterol Inhalation Powder, 100 mcg/50 mcg (Supplied by Teva Pharmaceuticals Ireland) to ADVAIR DISKUS® 100/50 (fluticasone propionate/salmeterol) Inhalation Powder, (GlaxoSmithKline) in Subjects With Asthma

- Subject requires the use of rescue medication during serial spirometry at Visit 2.
- Participant enrolls in another clinical trial, or is found to have previously enrolled in this clinical trial.

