## 10.4.6 Visit 3: End of Study (Day 29 ± 2)/Early Termination

- 1. Vital Signs: BP, HR, RR, and temperature will be collected.
- 2. Physical Exam: Perform an examination of head, ear, eyes, nose, throat, and lungs.
- 3. Urine Pregnancy Test: All females of childbearing potential will have a urine pregnancy test performed.
- 4. **Clinical Laboratory Testing:** All subjects will have a blood sample taken for hematology and clinical chemistry testing and a urine sample for urinalysis.
- 5. **12-Lead ECG**: Subjects will undergo a 12-lead ECG to screen for significant changes in cardiothoracic findings.
- 6. **Collect and Review Diary**: Diaries will be collected and reviewed for compliance with protocol requirements.
- 7. **Concomitant Medications**: Subjects will be questioned about any changes in concomitant medication use since the last visit. The subjects will also be questioned regarding washout of drugs prior to lung function testing.
- 8. Adverse Events: Subjects will be questioned about AEs since the last visit.
- 9. Spirometry: The final FEV1 measurements will be collected. The first FEV1 should occur at the same time of day as the FEV1 pre-dose measurement, respectively, collected at Visit 2 (± 2 hours). The remaining FEV1 measurements should be collected at following the preceding measurement.
- 10. Pulse Oximetry: Pulse oximetry will be measured during the spirometry testing.
- 11. Collect Study Product/Rescue Medication: All study product and rescue medication inhalers will be collected.

The

A Randomized, Multiple-Dose, Blinded, Placebo-Controlled, Parallel-Design, Multiple-Center, Clinical Study to Evaluate the Therapeutic Equivalence of Fluticasone Propionate and Salmeterol Inhalation Powder, 100 mcg/50 mcg (Supplied by Teva Pharmaceuticals Ireland) to ADVAIR DISKUS® 100/50 (fluticasone propionate/salmeterol) Inhalation Powder, (GlaxoSmithKline) in Subjects With Asthma

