## 10.5.14 Peak Flow Measurements

Subjects will measure twice-daily (morning and evening) peak expiratory flow (PEF; air flow in and out of the lungs) using a home spirometer/eDiary device. The subject will be dispensed the device upon entrance into the placebo run-in period. The same device will be used for the subject throughout their participation in the study. Subjects will be trained on the use of the device and PEF procedures at the Screening visit. At home PEF measurements are collected for interim safety monitoring only, and will not be included in statistical analyses.

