### 8.5 Methods for Handling Missing Data

For demographic and baseline characteristics, each variable will be analyzed using all available data. Subjects with missing data will be excluded only from analyses for which data are not available.

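### The mITT carry-forward rule for Day 29 FEV1 names the Early Termination visit as its source, but Protocol 10.2.5 waives spirometry at that visit while 10.4.6 lists it

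*SAP*

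**What the plan says.** The second co-primary endpoint is a morning pre-dose FEV1 at Visit 3, "after the last dose in the prior evening" (Protocol 11.5; SAP 6 agrees). Superiority to placebo on both co-primaries is tested in the mITT population (SAP 8.2.3). Protocol 8.4 makes superiority of both active products a requirement, so as to confirm that the study is sensitive.

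If a subject has no Visit 3 value, SAP 8.2.1 fills it in the mITT analysis with the "average of available predose assessments on the last post-baseline day (Day 2 through 32", provided at least one pre-dose FEV1 "assessment is available (e.g. the Early Termination visit". SAP 7, under the PP heading, also brings in lack-of-efficacy discontinuations by LOCF and points to 8.2.1.

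The protocol gives two instructions for the visit that would supply the value:

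- Section 10.2.5 asks early terminators to complete their next scheduled visit with all End of Study/Early Termination "activities except spirometry that does not need to be performed".
- Section 10.4.6, whose heading covers both Visit 3 and Early Termination, states at item 9: "Spirometry: The final FEV 1 measurements will be collected". It makes no legible exception for early terminators.

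On home measurements, Protocol 10.5.14 says: "At home PEF measurements are collected for interim safety monitoring only, and will not be included in statistical analyses".

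**The concern.** The analysis rule depends on a measurement that one part of the protocol requires and another part excuses. A site following 10.2.5 may skip it, and a site following 10.4.6 will take it. Whether an early terminator contributes to the mITT trough comparison then depends on which section the site read.

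Protocol 11.1 gives the SAP precedence where the two documents differ. That settles how data are analysed, but it cannot supply spirometry that was never performed.

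At stake is the Day 29 half of the superiority test. The reasons for early termination in 10.2.5 include worsening asthma and excessive rescue use. Early terminators are therefore unlikely to be a random subset, and their number may differ between placebo and active arms. A rule meant to keep them in the analysis would largely fail to do so.

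**Working it through.** **Step 1. Which FEV1 values could be carried forward?** The window opens on Day 2 and closes on Day 32.

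- Visit 2 serial spirometry (Day 1): outside the window.
- A scheduled clinic visit between Visits 2 and 3: none in the visit list of Protocol 10.0.
- Home peak flow: not FEV1, and not analysed.
- Visit 3/Early Termination spirometry: eligible, but required by 10.4.6 and waived by 10.2.5.
- Unscheduled visits: Protocol 10.2.6 mentions FEV1 there for worsening asthma, but only ad hoc.

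Under the waiver only the last source is left.

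**Step 2. What happens with no value?** SAP 8.5 excludes a subject with missing data from the analyses that need those data. An early terminator without spirometry therefore leaves the Day 29 comparison.

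**Step 3. When would an Early Termination value be taken?** Visit 3 spans Day 29 − 2 = 27 to Day 29 + 2 = 31. A subject who stops after Day 1 and attends the next scheduled visit on time is measured 27 − 1 = 26 to 31 − 1 = 30 days after Day 1. That is inside the window and off treatment.

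**Step 4. Scale.** The public text shows no sample size, SD, effect or dropout rate, so there is no plan figure to reproduce. All inputs below are assumptions.

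*(a) Waiver followed, nothing to carry.* With a share d of subjects lost, power = Φ(√(1 − d)·(z₀.₉₇₅ + z_power) − z₀.₉₇₅).

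- 80% design power: (1.960 + 0.842) = 2.802. At d = 5%, 78.0%; at d = 20%, √0.80 × 2.802 − 1.960 = 0.546, giving 70.7%.
- 90% design power: 88.5% at d = 5%, 82.6% at d = 20%.

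Any dropout allowance already in the design would reduce these losses. Bias from informative withdrawal is not captured.

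*(b) Waiver deleted, off-treatment values carried.* Assume completer means of +0.30 L (active) and +0.10 L (placebo), a difference of 0.200 L. A share f of an arm terminates early, and a share p of those has an off-treatment value v carried; the rest have none. With completer mean m, arm mean = ((1 − f)·m + f·p·v) / ((1 − f) + f·p).

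- Effective alternative therapy, v = +0.30 L, f = 20% placebo and 4% active, p = 25%: placebo = (0.80 × 0.10 + 0.05 × 0.30)/0.85 = 0.112; active stays 0.300; difference 0.188 L. At p = 100%: placebo 0.140, difference 0.160 L.
- Same v and p = 25%: 0.195 L with f = 10% v 4%, and 0.197 L with f = 6% v 2%.
- Active subjects off drug and doing badly, v = −0.20 L, placebo unchanged, f = 4%, p = 25%: active = (0.96 × 0.30 − 0.01 × 0.20)/0.97 = 0.295; difference 0.195 L.

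If instead a share d of subjects carries off-treatment values with no retained effect, replacing √(1 − d) by (1 − d) in (a) gives 75.9% to 61.1% from 80%, and 86.9% to 73.7% from 90%, for d = 5% to 20%.

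**The case against.** The best defence is that 10.2.5 is a specific exception to a general list. On that reading item 9 of 10.4.6 applies only to completers. SAP 8.2.1 works only where a value is available, and the Early Termination visit is given only as an example. SAP 8.5 deals with subjects who have nothing. Nothing then strictly contradicts anything.

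That reading is possible. It leaves the carry-forward rule almost empty, however, because the one visit it names is then a visit where the measurement is optional. Nor does it stop sites from following item 9, and Protocol 12.2.4 also has the Visit 3 source record completed for early terminators.

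A second objection is that collecting the value may do harm. Under the assumptions of step 4, off-treatment values with no retained effect cost more power than missing values do (61.1% against 70.7% at d = 20%, from 80%). This stands as a real cost. Both off-treatment mechanisms, a stopped active drug and effective alternative therapy on placebo, shrink the active-placebo difference, so the cost falls on the conservative side of a superiority test. Collection also keeps in the analysis the subjects whom the SAP says it will keep.

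Third, an on-treatment sensitivity analysis would be close to completers-only. It may itself be biased by informative withdrawal, and recovering 0.200 L in the model above is true by construction. It adds information but is not an unbiased reference.

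**Conclusion.** The conflict between Protocol 10.2.5, Protocol 10.4.6 item 9 and SAP 8.2.1 is real and rests on legible text. As written, the mITT carry-forward rule has no assured source. It should be fixed, though it does not undermine the design. The effect may be small: the number of early terminators is unknown, and in the examples of alternative therapy at p = 25% the difference falls by about 6% with 20% v 4% early terminators and by less than 3% with the lower rates.

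Four stronger readings are tempting and are not supported:

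- *The SAP has no on-treatment condition.* This cannot be judged. The sentence limiting eligible assessments is cut off at its upper day, and the mITT and PP definitions and SAP 8.7 are blank. A separate Protocol Deviations List also exists.
- *The SAP does not cover subjects with no value.* SAP 8.5 opens with "For demographic and baseline characteristics, each variable will be analyzed using all available data", but its next sentence, on exclusion where data are unavailable, is not limited on its face to baseline variables.
- *Off-treatment values could inflate superiority.* Giving v = −0.20 L to early terminators in both arms (20% v 4%, p = 25%) yields 0.295 − 0.082 = 0.212 L. That increase comes from poor disease course in placebo dropouts, who have no drug effect to lose.
- *PP equivalence is affected.* SAP 7 points to LOCF for lack-of-efficacy subjects, but the PP sentence in 8.2.1 is cut off. No such effect is claimed.

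**What to change.** 1. Delete the spirometry exception from Protocol 10.2.5, so that it agrees with 10.4.6 item 9 and SAP 8.2.1. The value LOCF relies on is then collected at a visit already planned.
2. Keep the primary mITT rule. Add one mITT superiority sensitivity analysis of the Day 29 endpoint, limited to values with a randomised dose the evening before (diary) and no restricted asthma medication started before the measurement (concomitant-medication dates). Leave out subjects without such a value.
3. Report by arm the number of mITT subjects with a Visit 3 value, an on-treatment carried value, an off-treatment carried value, and no value.

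Cost: a protocol wording amendment with IRB review (Protocol 12.2.3), spirometry for withdrawn subjects who attend, a short SAP addition, one derived flag from dates already collected, one extra model run and one count table. No visit is added. The primary analysis will contain more off-treatment values than under the waiver, and the sensitivity analysis must be read with its near-completers-only character in mind. Subjects who do not return will still have no value.
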